2.5. Statistical Analysis

All statistical analyses will be performed using the IBM SPSS Statistics v.31 software (IBM Corporation, Armonk, New York, NY, USA), and the results will be presented as means \pm standard deviations. Before the commencement of the study, a power analysis, using software package GPower 3.1, for statistical test "ANOVA: Repeated measures, within-between interaction (2 groups and 2 measures)" and effect size 0.30 (a err prob = 0.05) was performed. The statistical power analysis indicated that a total sample of 32 participants (16 participants in each group) would yield adequate power (0.90). The normality of the data will be examined using the Shapiro-Wilk test. Two-way analyses of variances (2-way ANOVAs) [2 groups (IG and CG) \times 2-time points (pre- and post-intervention)] with repeated measures on the "time-point" factor and Sidak pairwise comparisons will be applied to locate the significantly different means within and between groups. Independent t-tests will be also used to compare the percentage change (from pre- to post-measurement) between the two groups (IG and CG). The magnitude of the difference between measurements and groups will be examined using Cohen's *d* effect sizes (ES). The level of significance for all statistical analyses will be set at $p < 0.05$.

References

1. American College of Sports Medicine (ACSM) ACSM's Guidelines for Exercise Testing and Prescription. 9th ed. Lippincott Williams & Wilkins; Philadelphia, PA, USA: 2013. pp. 40–107.

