2.4. Procedure

The present study will be conducted according to the Declaration of Helsinki and approved by the Ethics Committee of the University of Thessaly. Prior to the start of the study, the participants: (a) will be informed about the experimental procedures and possible risks, (b) will be familiarized with the testing and exercise procedures and (c) will be signed an informed consent form. Following the initial information and familiarization procedure, the baseline measurements will be performed inside the workplace setting (during the working hours) by the same investigators and under the same conditions. The sequence of measurements will be: (1) health indices, (2) functional capacity indices (a. flexibility, b. balance, c. strength and d. aerobic capacity) and (3) dietary habits questionnaire. Before the commencement of the functional capacity tests, the participants will be performed a standardized 8 min warm-up protocol (3 min chair-based aerobic dance, 5 min of static and dynamic stretching for lower and upper body). Following the baseline measurements, the participants will be randomly assigned in two equal groups: the IG and the CG. In the present study, a parallel

randomized controlled design will be used to investigate the efficiency of the 6-month workplace combined intervention program (exercise and nutrition) on health, functional capacity and dietary habits indices in obese office workers. Specifically, a computer-generated list of random numbers will be used for the allocation of the participants in one of the two groups (IG or CG). The main investigator will be blinded for the allocated intervention during the entire period of data collection, and the participants were requested not to discuss their intervention with the main investigator.

During the study, the IG will be participate in a daily 6-month (5 times per week) combined intervention program consisting of exercise and nutrition; while the CG did not perform any intervention during the 6 months. The exercise program of the intervention will be supervised by three exercise instructors of the research team, and special exercise attendance books will be filled in to confirm the participants' exercise adherence, while the nutrition part of the intervention will be supervised by the two nutritionists of the research team. After the end of the 6-month period, the baseline measurements will be repeated in the same order and at the same time of day.

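### The planned group-by-time ANOVA is a change-score test; adjusting the 6-month value for the baseline already collected would usually be more precise, at the price of one degree of freedom

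*Combined protocol and SAP*

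**What the plan says.** Section 2.5 (Statistical Analysis) plans "Two-way analyses of variances (2-way ANOVAs" of group by time, with time as the repeated factor and Sidak pairwise comparisons. It adds a second between-group comparison: "Independent t-tests will be also used to compare the percentage change (from pre- to post-measurement) between the two groups (IG and CG"). It does not say which of the two decides an outcome. Results are to be given as means and standard deviations, with Cohen's d for the size of differences. No analysis uses the baseline value as a covariate, and no confidence interval for the between-group difference is mentioned.

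The sample size in the same section was computed for "ANOVA: Repeated measures, within-between interaction (2 groups and 2 measures"), with "effect size 0.30 (a err prob = 0.05) was performed". The result was "a total sample of 32 participants (16 participants in each group"), which "would yield adequate power (0.90"). The pre-post correlation used is not given.

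Section 2.4 (Procedure) fixes the order of events: "Following the baseline measurements, the participants will be randomly assigned in two equal groups: the IG and the CG". It also says that the same measurements are taken again after six months.

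**The concern.** With only two time points, the interaction test reduces to a comparison of mean change between the arms. A change score subtracts the whole baseline value, which amounts to fixing the regression slope of the 6-month value on baseline at 1. When SDs are similar at both times, the slope is ρ, which is below 1. Fixing it at 1 therefore adds noise unless ρ is close to 1. ANCOVA estimates the slope from the data. Because baseline is measured before randomisation, it is a legitimate covariate for every outcome measured at both times.

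At stake is precision in a trial planned with 16 per arm: wider intervals and lower power than the same data could give. The percentage-change t-test does not fill the gap, since dividing by baseline is not a regression adjustment for it.

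**Working it through.** **Inputs.** From section 2.5: effect size 0.30 (read as Cohen's f, since the plan gives no other label), α = 0.05, power 0.90, N = 32, two groups, two measures. From section 2.4: equal allocation after baseline. Assumptions: pre-post correlation ρ (not stated), equal SDs at both times, a common slope in both arms.

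**1. Reproduce the plan's figure.** For the within-between interaction, λ = f²·N·m/(1−ρ), with m = 2 and 1 and N−2 df. At ρ = 0.5, λ = 0.09 × 32 × 2 / 0.5 = 11.52 and power is 0.907. At N = 30 power is 0.887, so 32 is the smallest even N that reaches 0.90. Other values of ρ do not give 32: ρ = 0 needs 62, 0.3 needs 44, 0.7 needs 20. The plan's figure is reproduced under ρ = 0.5.

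**2. Identity with the change score.** For a difference in mean change of D SD, the t-test on change has λ = D²·(N/4)/[2(1−ρ)]. Setting this equal to the λ in step 1 gives D = 4f = 1.2 SD. Check: 1.44 × 8 / 1 = 11.52. In a simulated data set of 32, the interaction F and the squared t on change were both 1.6026.

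**3. Variance under ANCOVA.** In units of the outcome variance, the change score has variance 2(1−ρ) and the ANCOVA residual has 1−ρ². The large-sample ratio is (1+ρ)/2. Chance baseline imbalance multiplies the ANCOVA variance by 1 + 1/(N−4) on average, and residual df are N−3. At ρ = 0.5 and N = 32: 0.75 × (1 + 1/28) = 0.777. Simulation of 20,000 trials gave 0.782. The confidence interval is about 12% narrower.

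**4. Power at the plan's design point (D = 1.2, ρ = 0.5).** Averaging the noncentral F over chance imbalance:
- N = 32: 0.907 (planned test) against 0.961 (ANCOVA; 0.959 by simulation).
- N = 40: 0.959 against 0.988.
- Smallest even N for 0.90 with ANCOVA: 26 (power 0.911; N = 24 gives 0.884).

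**5. Range over ρ at N = 32.** The last column scales the effect so that the planned test has power 0.90.

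| ρ | Variance ratio, ANCOVA / change | CI width ratio | ANCOVA power |
|---|---|---|---|
| 0.3 | 0.67 | 0.82 | 0.976 |
| 0.5 | 0.78 | 0.88 | 0.956 |
| 0.7 | 0.88 | 0.94 | 0.932 |
| 0.8 | 0.93 | 0.97 | 0.918 |
| 0.9 | 0.98 | 0.99 | 0.904 |
| 0.95 | 1.01 | 1.006 | 0.896 |
| 0.98 | 1.03 | 1.014 | 0.892 |

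Break-even is where (1+ρ)/2 × (N−3)/(N−4) = 1, that is ρ = 2(N−4)/(N−3) − 1. This gives 56/29 − 1 = 0.93 at N = 32 and 72/37 − 1 = 0.95 at N = 40.

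**6. Adding workplace and sex.** Four workplaces (section 2.1) cost three df and sex one, so four beyond baseline. Simulation (8,000 trials per setting, N = 32, four equal workplaces, an even sex split, neither predicting the outcome) gave a variance ratio to the change score of 0.91 at ρ = 0.5, 1.03 at 0.7 and 1.11 at 0.8.

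**The case against.** The strongest reply is that the planned test already meets its own target (0.907 at N = 32), so nothing is broken, and that the size of any gain rests on a correlation the documents never give. Both statements stand. They make this an improvement rather than an error. They do not remove the expected gain over most of the plausible range of ρ.

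Several stronger readings are tempting and are not supported:

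- *ANCOVA is always more precise.* (1+ρ)/2 is a large-sample ratio. At N = 32 the advantage ends near ρ = 0.93.
- *The variance will fall by 25%.* At ρ = 0.5 and N = 32 the reduction is about 22%, and ρ = 0.5 is only the value that reproduces the sample size, not an estimate for any outcome here.
- *The reliability figures in section 2.3 (ICC 0.95 to 0.98) show that there is no gain.* They describe test-retest reliability, not correlation across six months. They do warn that very stable outcomes may gain little.
- *The planned estimate is biased by regression to the mean.* Under randomisation both arms regress equally in expectation. With 16 per arm the baseline difference has SE √(2/16) = 0.354 SD, and a chance imbalance of 0.5 SD would shift the change-score estimate by (1−ρ) × 0.5 = 0.25 SD at ρ = 0.5. That variability is already inside the change-score variance, so it is not a further harm.
- *Results will be shown only as means and SDs.* Section 2.5 also plans Cohen's d. What it does not mention is a between-group difference with a confidence interval.
- *More covariates would help further.* Step 6 shows that uninformative ones can cancel the gain. Covariates that do predict the outcome would recover some precision, but section 2.4 describes no stratification that calls for them.

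**Conclusion.** The point holds as a free improvement: no extra data, and one residual degree of freedom. The planned test is valid and unbiased; the loss is in efficiency. Under ρ = 0.5, baseline-only ANCOVA at N = 32 has about 0.78 times the variance, raises power from 0.907 to about 0.96 and would reach 0.90 with 26 participants. The figure of 26 measures the gain and is not a case for enrolling fewer. The benefit is large for ρ of 0.3 to 0.7, small at 0.8 to 0.9 and absent above about 0.93. The downside is bounded: even as ρ approaches 1 the interval would be only about 1.9% wider (√(29/28) = 1.018, times 1.0014 for the lost df). The results rest on reading 0.30 as f, equal SDs at both times and a common slope.

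**What to change.** In section 2.5, before outcome data are analysed, state that for each outcome the deciding between-group analysis is an ANCOVA of the 6-month value on group and the baseline value of that same outcome. Report the adjusted IG−CG difference with its 95% CI and p-value. Keep the 2×2 means, SDs and Cohen's d as description. State that the repeated-measures interaction and the percentage-change t-test do not decide the outcome. Do not add workplace and sex as routine covariates.

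The cost is a few sentences of wording, one residual df and a small penalty for chance imbalance (a factor of 1 + 1/28 on the variance at N = 32). No further measurement is needed, and the statistical package that the plan already names can fit the model.

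### Both planned between-group analyses need a 6-month value, and the plan does not say who will be measured, how groups are analysed, or what happens to missing values.

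*Combined protocol and SAP*

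**What the plan says.** Section 2.5 (Statistical Analysis) names two between-group analyses. The first is a two-group by two-time ANOVA on "2-time points (pre- and post-intervention" values, "with repeated measures on the 'time-point' factor and Sidak pairwise comparisons will be applied". The second is stated as "Independent t-tests will be also used to compare the percentage change (from pre- to post-measurement" between the groups. The software is SPSS v.31. The sample size assumes "effect size 0.30 (a err prob = 0.05) was performed" and concludes that "a total sample of 32 participants (16 participants in each group) would yield adequate power (0.90".

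Section 2.4 (Procedure) places randomisation after the baseline measurements and provides one later assessment: "After the end of the 6-month period, the baseline measurements will be repeated in the same order". It does not say for whom. On adherence, "special exercise attendance books will be filled in to confirm" participants' exercise adherence, but no rule connects attendance to any analysis set.

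Section 2.2.1 gives the intervention group 120 sessions, five days a week, and section 2.2.2 adds 12 nutrition sessions. Section 2.4 gives the control group no intervention. Section 2.1 expects 40 volunteers before eligibility is assessed.

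No section mentions analysis as randomised, an analysis population, drop-out, missing values, or measuring people who stop taking part.

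**The concern.** Each person has one baseline and one 6-month measurement. Anyone lost after randomisation therefore has a pre value only. Standard repeated-measures ANOVA in SPSS drops that person, and a percentage change cannot be calculated. The analysed set is then whoever returned for the second measurement, with nothing in the plan to protect the comparison if returning is related to baseline or to response.

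The two groups carry very different burdens, so the proportions lost may differ. If they do, and loss is related to outcome, the estimate no longer describes the groups as randomised. With no rule written down, decisions about who is measured and who is analysed could also be made after the losses are known.

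**Working it through.** **1. The plan's own figure.** Inputs from section 2.5: f = 0.30, alpha = 0.05, two groups, two measures, N = 32, power 0.90. The pre-post correlation ρ is not stated; 0.5 is assumed here, with sphericity correction 1. For the within-between interaction, λ = f² × N × 2/(1 − ρ), with 1 and N − 2 degrees of freedom. For N = 32, λ = 0.09 × 32 × 2/0.5 = 11.52 and power is 0.907. The smallest even N reaching 0.90 is 32, so the stated figure reproduces. It depends on ρ: the minimum N is 62 at ρ = 0, 44 at 0.3, 20 at 0.7 and 10 at 0.9.

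**2. Loss of precision (ρ = 0.5).**

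| Complete pairs | λ | Power |
|---|---|---|
| 40 | 14.40 | 0.959 |
| 36 | 12.96 | 0.938 |
| 32 | 11.52 | 0.907 |
| 26 | 9.36 | 0.835 |

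If 40 were randomised, 10% loss leaves 36 pairs and 20% leaves 32. The 26-pair row is relevant if only about 32 are randomised.

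**3. Size of a selection effect (assumed).** Suppose a share q of the intervention group stops, gains nothing relative to control and is not measured, while the others gain Δ. The as-randomised effect is (1 − q)Δ. The analysed people show Δ. The ratio is 1/(1 − q): 1/0.9 = 1.11, 1/0.8 = 1.25, 1/0.7 = 1.43.

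**4. False-positive rate (assumed).** Simulation with no true effect, 20 per arm, 4 lost from the intervention group only, t-test on change (equivalent to the interaction test), 20,000 runs:
- lost at random: no bias, error rate near 5%;
- loss moderately related to poor change (correlation 0.5): bias 0.17 SD of change, error rate 8%;
- the 4 worst responders lost: bias 0.33 SD, error rate 20%.

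**5. What baseline adjustment does.** It helps when loss depends on baseline. The slope of change on baseline is ρ − 1 = −0.5 (with equal pre and post SDs). If the retained intervention group starts 0.30 SD above control, the change comparison is shifted by −0.5 × 0.30 = −0.15 SD, and adjustment removes this. A simulation of baseline-dependent loss gave −0.15 SD and a 7.6% error rate unadjusted, against 0.00 and 5.4% adjusted. Adjustment is also more precise: the variance ratio to change scores is (1 − ρ²)/[2(1 − ρ)] = 0.75/1.00 = 0.75.

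It does not help in the situation of step 3. With 20 per arm, q = 20% and Δ = 1.0, the change-score and baseline-adjusted estimates both averaged 1.00, against (1 − 0.2) × 1.0 = 0.80 as randomised. With only two time points, a mixed model with a common baseline mean gives essentially the same estimate as ANCOVA on complete pairs.

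**The case against.** The strongest reply is that the plan never says it will analyse completers only. A reader might infer that the programme will be judged on those who stayed, but the documents do not support that. The methods exclude people without a 6-month measurement, not people with poor attendance. Section 2.4 sets no attendance condition on that measurement and places baseline testing at work in working hours, so someone who stops exercising could well be measured and would then stay in the analysis. This stands, and it limits the point to missing post values.

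Three other inferences also go too far.
- *Attendance books are meant to define a completers' set.* Their stated purpose is to confirm adherence, and nothing links them to exclusion.
- *Drop-out will fall mainly on the intervention group.* No rate is given for either group. Supervised sessions in working hours may limit loss, and controls who receive nothing may also leave.
- *Power will fall to 0.835.* That requires 26 complete pairs, whereas 40 volunteers are expected. Those 40 are counted before screening and are not described as a drop-out allowance, so neither 32 nor 40 can be taken as the number randomised. Extra participants would protect power but would not remove selection bias.

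What survives is that nothing in the plan commits to the measurement, the analysis as allocated, or a method for missing values.

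**Conclusion.** The point holds in this limited form: the named analyses exclude anyone without a 6-month value, and the plan has no safeguard for that case. Loss unrelated to baseline and outcome would cost only power. Loss related to either could bias the comparison: upwards by a factor of 1.11 to 1.43 in the illustration for 10% to 30% stopping, or downwards by 0.15 SD in the baseline-dependent example. These sizes rest on assumed loss rates, assumed mechanisms and an assumed correlation of 0.5; the documents supply none of them. The sample-size figure itself is not in error.

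A reader might also infer that moving to a mixed model would make the estimate unbiased. It would not if loss is related to the unseen outcome. Measuring people who stop is the main protection. The point should be addressed before the study starts, because the change is cheap and a rule set after losses are known is less credible.

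**What to change.** 1. In section 2.4, state that all randomised participants are invited to the 6-month measurements whatever their attendance. In section 2.5, state that they are analysed in their allocated group.
2. In section 2.5, make the between-group comparison baseline-adjusted: ANCOVA, or the equivalent SPSS MIXED model with a common baseline mean. Say that this is valid when loss depends only on group and baseline, and does not correct for loss related to the unseen outcome.
3. Add one sensitivity analysis that assumes no change from baseline for intervention participants with missing values. In the example with Δ = 1.0, 20% stopping and a control group that does not change, it gives 0.8 × 1.0 + 0.2 × 0 = 0.80, the as-randomised effect. Note that it is a single imputation resting on an untestable assumption and understates uncertainty.
4. State that attendance is used only for description or in a labelled supplementary analysis.

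The cost is a few sentences, one changed model and one extra analysis in software already planned, and a few follow-up contacts. The effect estimate may turn out smaller.

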Official Title: A combined workplace intervention including exercise and nutrition for health promotion in obese office workers: a randomized controlled study

NCT number (if available): It's not yet available.

Date of the document: 16/5/2026

1. Objective

Therefore, the main objective of this study is to design, implement, guide and evaluate the efficacy of a 6-month daily supervised workplace (during the working hours) combined intervention program including exercise (flexibility, balance, strength, aerobic capacity) and nutrition on selected health (body fat and circumferences, blood pressure, respiratory function, lipidemic profile), b) functional capacity indices (flexibility, static and dynamic balance, handgrip strength and aerobic capacity) and c) dietary habits (adherence to the Mediterranean diet, daily water consumption amount) of obese office workers. Another important objective of this study is to investigate the individualized responses per participant following the 6-month workplace intervention program. This is of fundamental importance since the individual characteristics of the participants may affect the efficiency of the intervention program and the generalization of study results in the whole population.

2. Methods

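### The within-group pre-post comparisons in 2.5 inherit an error variance pooled over IG and CG, and would be miscalibrated in both arms if change is more variable in the IG

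*Combined protocol and SAP*

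**What the plan says.** Section 2.5 specifies a 2 (group) × 2 (time) ANOVA with repeated measures on time. It adds that "Sidak pairwise comparisons will be applied to locate the significantly different means within and between groups". It also states that "Independent t-tests will be also used to compare the percentage change" between the arms, without saying whether the pooled or the unequal-variance form is meant. All tests use one threshold ("The level of significance for all statistical analyses will be set at" p < 0.05).

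The sample size is built on the group-by-time interaction: "effect size 0.30 (a err prob = 0.05) was performed", giving 32 participants (16 per arm) for power 0.90. Section 2.1 expects 40 volunteers. Section 2.4 allocates them to two arms of equal size and gives the CG no intervention.

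Section 2.5 names a normality check (Shapiro-Wilk). It names no error term for the within-group comparisons, no provision for unequal variances between the arms, and no alternative analysis. Section 1 makes individual response an objective, on the ground that "individual characteristics of the participants may affect the efficiency of the intervention program". No SD of change appears anywhere.

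**The concern.** With two time points, the error term of this ANOVA is the variance of the pre-post change, averaged over the two arms. That average is used for the interaction and, unless something else is specified, for the pre-post comparison within each arm.

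If people respond differently to the programme, that variation adds to the variance of change in the IG only, because the CG has no programme to respond to. The pooled term would then be too small for the IG and too large for the CG. The two within-arm tests would be tilted towards a significant change in the IG and none in the CG, a pattern easily read as efficacy. This happens even with equal arms and fully independent participants. If the IG also ended smaller than the CG, the interaction test would exceed its nominal level as well.

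**Working it through.** **1. The plan's own figure.** Inputs from 2.5: N = 32, m = 2 measures, f = 0.30, alpha 0.05. The pre-post correlation is not stated; 0.5 is assumed.

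- Noncentrality = N·m·f²/(1 − r) = 32 × 2 × 0.09 / 0.5 = 11.52.
- With 1 and 30 degrees of freedom, power is 0.907, so the stated 0.90 reproduces. N = 30 gives 0.887, so 32 is the smallest even total that reaches 0.90.
- The implied between-arm difference in change is √(4 × 11.52 / 32) = 1.2 SDs of change. At r = 0.5 the SD of change is √(2(1 − 0.5)) = 1 baseline SD, so this is also 1.2 baseline SDs.

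**2. What SD ratio is plausible.** The documents give none. Let s be the SD of individual response in baseline-SD units, independent of natural change. Then the IG:CG ratio of SDs of change is √(2(1 − r) + s²) / √(2(1 − r)). Take s = 0.6, half of the 1.2 planning difference (an assumption):

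- r = 0.5: √1.36 / √1 = 1.17
- r = 0.9: √0.56 / √0.2 = 1.67
- r = 0.95: √0.46 / √0.1 = 2.1

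The ratio 1.17 belongs to the correlation at which the stated power reproduces. Ratios of 1.5 and 2 are kept as a sensitivity range.

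**3. Error in the standard errors, equal arms.** With the CG SD set to 1 and the ratio k, the pooled SD is √((k² + 1)/2).

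- k = 1.17: √1.18 = 1.09, which is 0.93 of the true IG value and 1.09 times the true CG value.
- k = 1.5: 1.27, which is 0.85 of the IG value and 1.27 times the CG value.
- k = 2: 1.58, which is 0.79 of the IG value and 1.58 times the CG value.

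**4. Type I error.** Simulated normal changes, no mean change in either arm, two-sided nominal 5%, 16 per arm:

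| SD ratio IG:CG | IG pre-post, pooled | CG pre-post, pooled | Interaction, pooled |
|---|---|---|---|
| 1 | 5.0% | 5.0% | 5.0% |
| 1.17 | 6.7% | 3.4% | 5.0% |
| 1.5 | 9.4% | 1.5% | 5.1% |
| 2 | 12% | 0.4% | 5.3% |

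With 20 per arm the results are almost the same. The pattern of IG significant and CG not significant arises in just under 5% of null trials at ratio 1, about 9% at 1.5 and about 12% at 2. With each arm's own SD of change, both within-arm tests stay at about 5% at every ratio. Welch on the change also stays at about 5%.

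**5. Unequal completers.** The documents give no dropout figure, so the splits are assumptions.

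- 16 IG / 20 CG: the pooled interaction rejects 5.4%, 6.2% and 7.0% at ratios 1.17, 1.5 and 2.
- 12 IG / 20 CG: about 7.6% and 9.6% at ratios 1.5 and 2.
- 20 IG / 16 CG: the error goes the other way, to about 4% at ratios 1.5 and 2.

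**6. Sidak.** With two time points there is one pre-post comparison per arm. The Sidak level for one comparison is 1 − (1 − 0.05)¹ = 0.05, so the correction neither causes nor cures the problem.

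**The case against.** The strongest case against is that the plan's randomised comparison is sound as designed. The arms are equal, the trial is powered on the interaction, and that test holds its level. This stands. A reader might infer that the ANOVA as a whole is invalid; the documents do not support that, because interaction inflation needs both a larger IG variance and fewer IG completers.

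A reader might also infer that the plan expects greater variability in the IG, so that IG change *is* over-called. Section 1 says only that individual characteristics may matter, and treats this as a question to investigate. At ratio 1 nothing is distorted, and if the CG varied more the direction would reverse. The point is conditional.

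It is tempting to lead with ratios of 1.5 to 2. Under the response SD assumed here they need a correlation near 0.9 or above, whereas the stated power reproduces at 0.5, where the ratio is 1.17 and the distortion modest. A planning correlation need not be the true one, so the larger ratios remain a range and not a base case. The test-retest ICCs in 2.3 do not settle it, because they are not six-month correlations.

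Two further limits stand. Nothing in 2.5 says that efficacy will be concluded from a significant IG change beside a non-significant CG change. And the plan does not say that its t-tests are pooled; it is silent.

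What the objection does not remove is that the within-group comparisons are a prespecified output, are not subordinated to the interaction, and rest on an equal-variance assumption for which the plan has no fallback.

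**Conclusion.** The point holds in conditional form and for the within-group comparisons. The pooled error term follows from the method named in 2.5; the text does not state it. If the SD of change is larger in the IG, the IG pre-post test is too liberal and the CG test too conservative: from about 6.7% and 3.4% at a ratio of 1.17 to 12% and 0.4% at a ratio of 2, with 16 per arm. The interaction stays at or below about 5.3% over that range with equal arms, and becomes liberal only if the IG ends smaller than the CG.

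These figures assume normal changes, independent participants, two-sided tests and SD ratios that are not in the documents. They do not show that the trial's main comparison is wrong. This is a cheap improvement to the analysis section, not a defect of the design.

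**What to change.** In 2.5, state that:

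- the efficacy conclusion rests on the between-arm contrast of change, by a Welch test or by a model with arm-specific variances and Satterthwaite degrees of freedom;
- within-arm change is descriptive support, with an interval computed from that arm's own SD of change;
- the independent t-tests use the unequal-variance form throughout, without a preliminary variance test.

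The cost is a few lines of wording. If the variances are in fact equal, power for the 1.2-SD difference is essentially unchanged at 16/16 (about 0.91 either way) and falls by under 1 point at 12/20 (0.887 to 0.880). Within-arm intervals lose degrees of freedom (15 instead of 30 at 16 per arm). For an assumed within-arm change of 0.7 SD, that lowers power from 0.773 to 0.745 at 16 per arm, and from 0.863 to 0.845 at 20 per arm.

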2.1. Participants

40 obese office workers (males and females), after announcements by the research team in four workplaces in the region of Western Thessaly in Greece, are expected to express interest in participating in the present study. The participants will be assessed for eligibility according to six inclusion criteria. In more detail, the participants: 1) should have at least 8 h per day in the office, 2) should have BMI value ≥ 30 kg/m², 3) should not have chronic diseases (physical or mental), 4) should not use any medication, 5) should not have injuries (in lower or upper body) the last 6 months and 6) should not participate in organized exercise programs or nutrition intervention during the last 6 months. Prior to the start of the study, the demographic, anthropometric, and working characteristics of the participants will be assessed using the American College of Sports Medicine (ACSM) health history questionnaire.

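### No test is declared decisive for efficacy: each outcome gets an interaction test, within- and between-group pairwise tests and a percentage-change t-test, all at p < 0.05, and the within-group tests do not use the control group

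*Combined protocol and SAP*

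**What the plan says.** Section 2.5 (Statistical Analysis) lists three layers of testing for each outcome.

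- A two-way ANOVA, group (IG, CG) by time (pre, post), with repeated measures on time.
- Pairwise follow-up: "Sidak pairwise comparisons will be applied to locate the significantly different means within and between groups". It is not made conditional on a significant interaction.
- A further comparison: "Independent t-tests will be also used to compare the percentage change (from pre- to post-measurement) between the two groups".

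One threshold covers everything: "The level of significance for all statistical analyses will be set at" p < 0.05. The sample size is based on the within-between interaction, with "effect size 0.30 (a err prob = 0.05) was performed", giving 16 per group for power 0.90. Section 2.4 (Procedure) describes a parallel design in which "the participants will be randomly assigned in two equal groups: the IG and the CG". Section 1 (Objective) states the aim as efficacy over many indices and names no primary outcome.

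Nowhere does the plan say which of these results decides whether the programme worked on an outcome, which are supportive, or what is concluded if they disagree.

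**The concern.** A parallel randomised trial shows efficacy by comparing groups. Three of the four kinds of result planned here do that: the interaction, the between-group comparison at 6 months, and the percentage-change t-test. The fourth, the pre-post comparison inside a group, does not. Anything that moves both groups alike (season, being measured, repeated testing) makes it significant, and a significant change in IG beside a non-significant one in CG is not a test of the difference between them.

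The Sidak adjustment does not help as it is usually applied. With two groups and two time points, each simple comparison is a family of one.

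Without a stated rule, a positive claim for an outcome can rest on whichever of four results is significant, and a reader of the final report could not tell whether that choice was made in advance.

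**Working it through.** **Inputs from the documents.** α = 0.05 for every analysis; f = 0.30; N = 32 (16 per group); 1:1 allocation; two groups, two time points.

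**Assumptions, because the documents give no figures.** Pre-post correlation ρ (0.5 unless stated); baseline coefficient of variation (CV) 10–35%; a time drift common to both groups of 0–0.5 SD; two-sided t-tests; normal data. Rates come from simulation with 20,000–40,000 trials per setting, or from the formulas shown.

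**1. The plan's own figure.** For the interaction, λ = f²·N·m/(1 − ρ), with m = 2, df = 1 and N − 2. At ρ = 0.5, λ = 0.09 × 32 × 2 / 0.5 = 11.52 and power is 0.907; N = 30 gives 0.887. So 32 is reproduced. This effect is a between-group difference in change of 1.2 SD: the SD of change is √(2(1 − ρ)) = 1, and (1.2 × √(16/2))² = 11.52.

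**2. Sidak in a 2 × 2 layout.** Adjusted p = 1 − (1 − p)^k. Each within-group comparison of two time points, and each between-group comparison at one time point, has k = 1, so adjusted p = p.

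**3. Within-IG test, no programme effect, common drift δ (in SD).** The paired t-test has noncentrality δ√16 / √(2(1 − ρ)) on 15 df. Call its rejection rate p. The groups are independent, so IG significant with CG not significant has probability p(1 − p).

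| δ | ρ | noncentrality | within-IG significant | IG significant, CG not | interaction |
|---|---|---|---|---|---|
| 0.3 | 0.5 | 1.20 | 20% | 16% | 5% |
| 0.3 | 0.7 | 1.55 | 31% | 21% | 5% |
| 0.5 | 0.5 | 2.00 | 47% | 25% | 5% |
| 0.5 | 0.7 | 2.58 | 67% | 22% | 5% |

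**4. False positives per outcome, no programme effect and no drift.**

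| Results allowed to count | Rate |
|---|---|
| Interaction only | 5% |
| Interaction or percentage change | 5.3–6.3% |
| Interaction, percentage change or within-IG | 8.3–9.3% |
| Those three or the post-only between-group comparison | 12.0–13.5% |

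The percentage-change test adds 0.3–1.3 points. The pairwise tests add the rest.

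**5. Power of the percentage-change test at the planned effect (ρ = 0.5, 16 per group; interaction about 0.91).**

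| Baseline CV | Additive increase | Additive decrease |
|---|---|---|
| 15% | 0.86 | 0.92 |
| 25% | 0.77 | 0.90 |
| 35% | 0.58 | 0.79 |

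If change is proportional to baseline, the percentage-change test has 0.89–0.91 against 0.80–0.90 for the interaction. For additive increases the two tests disagree in 5%, 14% and 33% of trials at CV 15%, 25% and 35%. Nearly all of this is the interaction succeeding and percentage change failing; the reverse is about 0.2%.

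**6. Power after the fix.** With the effect scaled so that the interaction keeps 0.907 at N = 32, baseline-adjusted ANCOVA under an additive effect has about 0.98 at ρ = 0.3, 0.96 at ρ = 0.5 and 0.92–0.93 at ρ = 0.8.

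**The case against.** The best defence is that a main test exists in all but name. The study is powered on the interaction, the ANOVA comes first, and the t-tests are introduced as an addition. That is a fair reading of intent, but the analysis text never gives the interaction that role or makes the pairwise tests depend on it.

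Three stronger readings are tempting, and the documents do not support them.

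- *The percentage-change t-test is the main source of false positives.* It is not; it adds about 1 point per outcome. At the planned effect, for additive increases, its disagreements with the interaction are almost all failures to reject, which give no extra route to a claim.
- *Every added test is weaker or irrelevant to efficacy.* The loss of power for percentage change is specific to additive effects, mainly increases. The comparison of groups at 6 months is a valid efficacy test under randomisation: against about 0.91 for the interaction, it has power 0.97 at ρ = 0.3, equal power at ρ = 0.5 and 0.54 at ρ = 0.8.
- *Large drift is to be expected.* The documents give no drift, CV or ρ. Section 2.4 plans familiarisation with the tests before baseline, and repeat measurement in the same order and at the same time of day. These should reduce learning effects, though not seasonal ones.

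It is also fair to say that one sentence naming the interaction would close the gap. ANCOVA is preferable on power but is not the only adequate repair.

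**Conclusion.** The concern stands in this form: four kinds of result per outcome share one threshold with no declared decisive test, and one kind, the within-group comparison, cannot show efficacy.

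The absence of a rule, the failure of within-group tests to use the control, and the lack of any Sidak correction when it is applied family by family follow from the text and the design. The sizes are conditional. The 20–67% for the within-IG test, and 16–25% for IG significant with CG not, require a common drift of 0.3–0.5 SD and ρ of 0.5–0.7. The 9% and 13% per-outcome rates require that any of the listed results be allowed to support a claim, which the plan neither states nor rules out. The loss of power for percentage change is a possibility that depends on the scale and direction of each outcome, not a general defect.

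This should be corrected before analysis. It does not undermine the design or the sample size. Multiplicity across the many outcomes is a separate matter and is not counted here.

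**What to change.** In section 2.5, state that efficacy for each outcome is concluded solely from one between-group test: the difference between IG and CG at 6 months adjusted for the baseline value (ANCOVA), with its 95% CI. Report within-group changes and percentage changes descriptively, with 95% CIs and no efficacy claim. If the team prefers to keep the interaction, the same sentence should name it as the only decisive test.

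Where a relative effect is wanted for a strictly positive outcome, log(post) adjusted for log(baseline) is an option, not a requirement.

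The cost is a change of wording and fewer p-values to report. No extra participants or measurements are needed. Under the additive model above, N = 32 gives ANCOVA power of about 0.92–0.98 for ρ from 0.8 down to 0.3, where the interaction has 0.91.
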